4.0 SUBJECT SELECTION

4.1 INCLUSION CRITERIA

Subject eligibility should be reviewed and documented by an appropriately qualified member of the Principal Investigator's (PI's) study team before participants are included in the study.

1. Successful completion of Study TTP488-301 through the Month 18 Visit without ongoing SAEs or history of serious adverse drug reactions during study TTP488-301.
2. Patients must enroll in the present study within 7 days of completion of study TTP488-301.
3. Evidence of a personally signed and dated informed consent document indicating that the subject (or a legally authorized representative) and caregiver/informant has been informed of all pertinent aspects of the study. Participants must be able to provide assent (where this is in accordance with local laws, regulations and ethics committee policy) and assent may be re-evaluated during the study at regular intervals.
4. Participants and caregiver/informants who are willing and able to comply with scheduled visits, treatment plan, laboratory tests, and other study procedures.
5. The subject must have a reliable caregiver/informant with regular contact (i.e., 10 hours a week as a combination of face-to-face visits and telephone contacts are acceptable) who will facilitate the subject's full participation in the study. Caregivers/informant must have sufficient subject interaction to be able to provide meaningful input into the rating scales administered in this study where caregiver/informant input is required, in particular the CDR and evidence of this should be documented in source documentation. Participants who reside in assisted living facilities are permitted provided that they meet caregiver/informant criteria.
6. Participants and caregiver/informants must be able to read, write, and speak the language in which psychometric tests are provided with visual and auditory acuity (corrected) sufficient to allow for accurate psychometric testing.

7. Subject must be able to ingest oral medications.

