1.4 Randomization

The open-label extension study was not randomized.

It is noted that TTP488-301 was randomized, and the randomization scheme for TTP488-301 is used to identify what will be called "treatment groups" in this SAP. The completers of TTP488-301 who are enrollees of TTP488-303 will be designated as

- Crossing over from placebo to azeliragon or
- Continuing on azeliragon.

Randomization in TTP488-301 had balanced allocation (1:1) between active and placebo. Dropouts were not allowed to be replaced.

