1.5 Study Design

This is an open-label extension study in patients with mild Alzheimer's disease who have successfully completed participation in the azeliragon Phase 3 TTP488-301 (STEADFAST) trial. Patients may receive azeliragon 5 mg/day for up to 2 years.

Participants were required to continue to be on SoC of a stable background acetylcholinesterase inhibitor therapy and / or memantine and continue the therapy for the duration of the trial, unless the investigator judges that the dose needs to be reduced or stopped due to a safety and/or tolerability reason.

Subjects were expected to participate in approximately 9 outpatient visits including baseline which is the same visit at the Month 18 visit in the TTP488-301 study.

Protocol TTP488-301 included two studies with a common infrastructure (A-study and B-study). Participants from either study are allowed to roll over into this open-label extension study.

A-study is conducted at multiple sites in the US and Canada. B-study is conducted at multiple sites in the US, Canada, Ireland, UK, South Africa, New Zealand, and Australia.

This study was terminated prematurely before participation outside of the US and Canada began; therefore, this study is conducted at multiple sites in the US and Canada.

The overall structure of the study includes the following periods:

Baseline Study Period: (Month 18 visit of TTP488-301): At the Month 18 visit of TTP488-301, subjects who met eligibility requirements were offered enrollment into this open-label extension study. Subjects had baseline assessments for efficacy and safety measures, including PK assessments.

Treatment Period: (Day 1 (Month 18 visit of TTP488-301) — Month 24): Subjects were treated with open-label azeliragon 5 mg QD. Efficacy and safety measures were taken. Blood samples were taken and subjects have assessments for safety and PK.

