5.1.1 Statistical Methodology for Primary Efficacy Analysis

The primary descriptive analysis will be done on change from baseline in ADAS-cog and on change from baseline in CDR-sb.

Analysis of covariance (ANCOVA) will be done to compare those patients who were randomized to azeliragon in TTP488-301 with those who were randomized to placebo. The ANCOVA will include baseline measure as a covariate and treatment arm from TTP488-301; a main-effects model will be used.

Descriptive analysis will be applied to those patients who were treated with placebo in TTP488-301 to compare the profile during TTP488-301 with that of the profile in TTP488-303.

Descriptive statistics will be applied to the total patient population without regard for prior treatment.

Analyses will include data from the 18-month period from TTP488-301 with continuation for the available visit data from TTP488-303.

Additional supportive analyses will be done for which data displays are not planned.

Descriptive summaries will be produced of the observed values and change from Baseline in efficacy variables by treatment group at each individual time point and at endpoint (final on-treatment assessment for each subject).

For statistical analyses, 95% confidence intervals will be produced for the least-squares means (LSM) in each treatment group.

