5.2 Disposition, Demography, and Baseline Characteristics

A tabulation of subject disposition will be presented, including the number each population group, the number dosed in each population group, the number who withdrew prior to completing the study, and reasons for withdrawal.

Demographic and baseline characteristics (disease history, medical history, and prior treatments for AD) will be summarized for all enrolled patients and for the FAS. No formal statistical comparisons will be performed. Summaries of continuous variables will include number of patients, mean, median, minimum, maximum, and standard deviation. Summaries of categorical variables will include numbers of patients in each category.

The variables to be summarized will include:

- Age, gender, race, and ethnicity
- Weight, height, BMI
- Years since diagnosis of AD
- MMSE category (mild or moderate)
- MMSE, ADAS-cog, CDR-sb, CDR-global, ADCS-ADL
- ApoE status
- Education level
- Background AD medications (ACHEI, Memantine, Both).

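### The ANCOVA of the former TTP488-301 arms adjusts only for the baseline score, although the groups are completers who chose to continue and other baseline factors are already in hand

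*SAP*

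**What the plan says.** SAP 5.1.1 states the comparison: "Analysis of covariance (ANCOVA) will be done to compare those patients who were randomized to azeliragon in TTP488-301 with those who were randomized to placebo". Its model follows: "The ANCOVA will include baseline measure as a covariate and treatment arm from TTP488-301; a main-effects model will be used". The planned intervals are 95% confidence intervals for the least-squares mean in each group. SAP 5.1.2 carries a similar model to MMSE, ADCS-ADL, NPI and plasma A-beta, and an ANCOVA with its own baseline score to DEMQOL-Proxy.

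The groups are defined after randomisation. SAP 1.4 begins "The completers of TTP488-301 who are enrollees of TTP488-303 will be designated as" and then names two groups, those crossing over from placebo and those continuing on azeliragon. Protocol 4.1 requires "Successful completion of Study TTP488-301 through the Month 18 Visit without ongoing SAEs or history of serious adverse drug reactions during study TTP488-301".

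SAP 5.2 lists age, ApoE status, education level and background AD medication among the variables to be summarised at baseline, with no formal comparisons. SAP 1.5 adds that "Protocol TTP488-301 included two studies with a common infrastructure", the A-study and the B-study. No section puts any of these into a model or specifies a covariate-adjusted sensitivity analysis.

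On the baseline score, SAP 5 defines baseline as the last value before treatment in TTP488-303. SAP 6.1 says two baselines will be used, one before double-blind dosing and one before open-label dosing. SAP 5.1.1 does not say which one is the covariate.

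**The concern.** In TTP488-301 the arms were comparable by design. In the extension they are what remains after three filters: completing 18 months, meeting safety-related entry criteria, and choosing to continue. Each filter acts after randomisation and may work differently on drug and on placebo. If it does, the arms can differ on characteristics that also affect later decline. A model holding only the baseline score removes such a difference only so far as the score carries it.

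At stake are the least-squares means, their intervals and any arm difference a reader takes from them. SAP 4.1 labels ADAS-cog and CDR-sb co-primary and expects the efficacy evaluation to be informative.

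Pre-specification matters too. SAP 5.1.1 foresees supportive analyses without planned displays, SAP 5.1.3 leaves subgroups post hoc, and SAP 5.5 allows further analyses that may go unreported. An adjusted model chosen later, with open-label data in view, would carry less weight than one fixed now.

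**Working it through.** The documents give no standard deviation, effect size, roll-over rate or baseline imbalance for this comparison, so there is no plan figure to reproduce. From the documents: TTP488-301 planned 800 patients (SAP 1.6) allocated 1:1 (SAP 1.4), so at most 800 / 2 = 400 per former arm. Every other input below is an assumption.

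**1. Precision.** Adding covariates with partial R-squared r multiplies the residual SD, and so the interval width, by sqrt(1 - r), ignoring the few degrees of freedom lost. This applies to the per-group intervals the SAP plans as well as to a difference, and to CDR-sb as well as ADAS-cog.

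- r = 0.02: sqrt(0.98) = 0.990, 1.0% narrower
- r = 0.05: sqrt(0.95) = 0.975, 2.5% narrower
- r = 0.10: sqrt(0.90) = 0.949, 5.1% narrower

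**2. Bias from one omitted binary factor.** Bias = (difference in its prevalence between arms) x (its effect on the outcome, given the baseline score). With 10 percentage points and 2 ADAS-cog points: 0.10 x 2 = 0.2 point. Over a grid of 2-15 percentage points and 0.5-3 points the range is 0.02 x 0.5 = 0.01 to 0.15 x 3 = 0.45 point.

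**3. Bias against sampling error.** Half-width of a 95% interval for the arm difference = 1.96 x SD x sqrt(2/n), with n per arm.

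| n per arm | SD 6 | SD 8 | SD 10 |
|---|---|---|---|
| 400 | 0.83 | 1.11 | 1.39 |
| 300 | 0.96 | 1.28 | 1.60 |
| 200 | 1.18 | 1.57 | 1.96 |
| 100 | 1.66 | 2.22 | 2.77 |

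The largest bias on the grid, 0.45, is below the smallest half-width, 0.83. A bias of 0.2 is 0.2/2.77 = 7% to 0.2/0.83 = 24% of a half-width.

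**4. Simulation.** Assumptions: 400 per arm randomised, about 65% enrolling (about 520 in all), true arm effect zero, residual SD 7, 2,000 runs. In all but the first row, roll-over in the active arm depends on a measured binary factor, an unmeasured factor, or both. The unmeasured factor is worth 1 point per SD. Simulation error is about 0.01 point for bias (2 x 7 / sqrt(520) = 0.61; 0.61 / sqrt(2000) = 0.014) and 0.5 percentage point for coverage (sqrt(0.95 x 0.05 / 2000) = 0.005).

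| Scenario | Imbalance (points of %) | Bias, baseline only | Coverage | Bias, factor added | Coverage |
|---|---|---|---|---|---|
| Effect 2, no differential roll-over | 0.1 | 0.02 | 95.6% | 0.02 | 95.5% |
| Effect 2 | 3.9 | -0.06 | 95.5% | 0.02 | 95.7% |
| Effect 2 | 7.7 | -0.18 | 94.3% | -0.03 | 95.0% |
| Effect 3 | 11.5 | -0.35 | 91.2% | -0.02 | 95.0% |
| Effect 2, plus unmeasured selection | 7.8 | -0.29 | 93.0% | -0.14 | 94.8% |
| Unmeasured selection only | 0.1 | -0.19 | 94.0% | -0.19 | 94.0% |

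The change in bias on adding the factor agrees with step 2. In the third row it is 0.18 - 0.03 = 0.15, against 0.077 x 2 = 0.154. The omission matters only if roll-over differs by arm, and adjustment removes only the measured part.

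**The case against.** A small model is a defensible choice for a descriptive, unpowered extension. SAP 2 states no hypotheses and SAP 5.1 allocates no alpha. Protocol 9.0 places the key analysis in an integrated plan that was not supplied, so whether that plan carries covariates cannot be checked. Baseline tables under SAP 5.2 and displays by former arm should make imbalance on these factors visible. All of this stands, and it limits the weight of the point. It does not remove the case for fixing the adjusted model in advance, because this ANCOVA is planned in its own right.

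Four stronger readings are tempting, and the documents do not support them.

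- **That the comparison is biased, or that known prognostic factors were left out.** No section gives roll-over by arm, an imbalance, or an effect of any listed factor on decline. Bias is a risk only.
- **That the trial's main efficacy result is affected.** Efficacy is a secondary objective here and the key analysis lies elsewhere.
- **That stratification factors were omitted, or that leaving out the A/B term is a clear error.** Neither document describes stratified randomisation. The two studies shared an infrastructure. SAP 1.5 also says "This study was terminated prematurely before participation outside of the US and Canada began", so the country difference between A and B largely disappears. A missing study term would bias the arm contrast only if study predicted outcome and roll-over varied by both arm and study.
- **That covariates would restore the randomised comparison.** The last two simulation rows show otherwise.

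**Conclusion.** The point holds as a minor, inexpensive improvement. The two-term model uses less than is available for a comparison that randomisation no longer protects, and no adjusted analysis is specified.

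The size rests on assumed inputs: intervals 1-5% narrower if the covariates explain 2-10% of residual variance, and about 0.2 ADAS-cog point of bias removed at a 10-point imbalance in a factor worth 2 points. On a 0-70 scale that is small, and below the sampling error at any plausible number enrolled. If roll-over did not differ by arm, there would be essentially no bias to remove. Type I error and sample size are not affected.

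The unspecified baseline covariate belongs to the same correction. If the Month 18 score of TTP488-301 is used, the model conditions on a value measured after 18 months of randomised treatment. If the score before double-blind dosing is used, it does not. The estimate means something different in each case, and adding covariates does not settle the choice.

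**What to change.** In SAP 5.1.1:

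- Pre-specify, for ADAS-cog and CDR-sb, an ANCOVA with baseline score, former arm, age, ApoE4 carrier status, education and background AD medication. Take the four added factors at their values before TTP488-301 randomisation, so that none can have been changed by the earlier treatment. Source study (A/B) may be added as an optional factor.
- Keep the two-term model as a supportive analysis and report both.
- State which of the two baselines in SAP 6.1 is the covariate. If it is the Month 18 score, say that the comparison is conditional on the state reached after blinded treatment.
- Label the comparison of former arms as non-randomised and descriptive. Tabulate the TTP488-301 baseline characteristics of enrollees and non-enrollees by arm, so that readers can judge the selection.
- Say how subjects with a missing covariate are handled, and report how many there are.

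The cost is SAP wording, a few model degrees of freedom and possibly some subjects lost to missing covariates. SAP 5.2 already plans to summarise these factors, so no new data collection is needed.

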5.1.2 Statistical Methods for Secondary Variables

Secondary and exploratory endpoints that are measurement variables will use similar statistical methodology to the methodology used for primary analysis.

Subgroup analyses may be done as identified subsequently; data-driven subgroup analyses may be done as exploratory analyses.

For change from Baseline in plasma concentrations of A β species, an ANCOVA analysis similar to that described for the co-primary endpoints with baseline plasma concentrations of A β species as a continuous covariate will be performed.

For change from Baseline in MMSE, an ANCOVA analysis similar to that described for the co-primary endpoints will be performed, with baseline MMSE as a continuous covariate.

For change from Baseline in ADCS-ADL, an ANCOVA analysis similar to that described for the co-primary variables of interest will be performed, with baseline ADCS-ADL as a continuous covariate.

For change from Baseline in NPI, an ANCOVA analysis similar to that described for the co-primary endpoints will be performed, with baseline NPI as a continuous covariate.

Individual item responses on the RUD questionnaire and the total caregiver time spent assisting the patient based on the RUD questionnaire will be summarized by treatment group.

For change from baseline in DEMQOL-Proxy total score, an ANCOVA analysis with Baseline DEMQOL-Proxy as a continuous covariate will be performed.

If the distribution of any of the above parameters, key secondary, or other secondary endpoints does not appear to be normally distributed, the rank analogues will be utilized.

5.1.3 Subgroup Analyses

Subgroups may be defined post-hoc.

5.2 Disposition, Demography, and Baseline Characteristics

A tabulation of subject disposition will be presented, including the number each population group, the number dosed in each population group, the number who withdrew prior to completing the study, and reasons for withdrawal.

Demographic and baseline characteristics (disease history, medical history, and prior treatments for AD) will be summarized for all enrolled patients and for the FAS. No formal statistical comparisons will be performed. Summaries of continuous variables will include number of patients, mean, median, minimum, maximum, and standard deviation. Summaries of categorical variables will include numbers of patients in each category.

The variables to be summarized will include:

- Age, gender, race, and ethnicity
- Weight, height, BMI
- Years since diagnosis of AD
- MMSE category (mild or moderate)
- MMSE, ADAS-cog, CDR-sb, CDR-global, ADCS-ADL
- ApoE status
- Education level
- Background AD medications (ACHEI, Memantine, Both).

5.3 Analysis of Safety Data

5.3.1 Adverse Events

Adverse events reported in this study will be coded using MedDRA®, Version 16.0, or later. Coding will be to the lowest level terms (LLT). The verbatim text, the preferred term, and the primary SOC will be listed in subject listings. Summaries that include frequencies and proportions of patients reporting AEs will include the preferred terms and the SOCs. Summaries will include TEAEs by severity and by relationship to study medication.

Adverse event summaries will be constructed displaying AEs in decreasing order of total frequency according to the numbers of subjects reporting the AE (not the number of reports).

- Number (percent) of subjects reporting TEAE by treatment and overall in accordance with variables listed in Section 4.2.1.

Supportive listings will be constructed that includes the subject identification, the treatment group (based on randomization from TTP488-301 and the pooled group of enrollees from TTP488-303), TEAEs, MedDRA terms, seriousness, severity, causality, elapsed time to onset, duration, and outcome.

Methodology for AESIs will follow the same methodology for TEAEs.

5.3.2 Vital Signs

Subjects with vital signs meeting the criteria in Section 10 of this SAP for values of potential clinical concern will be flagged and summarized. Proportions of subjects with vital signs of potential clinical concern will be examined for the treatment groups.

No formal inferential statistics will be applied to the vital signs data.

For each post-Baseline assessment, descriptive statistics are provided for the assessment value and the change from Baseline to the assessment with mean, median, standard deviation, minimum, and maximum at each assessment time.

5.3.3 Routine Clinical Laboratory Measurements

Because “exacerbations” of pre-existing abnormalities in laboratory analytes are examined using clinical judgment and are reported as TEAEs, additional analysis on TEAVs is limited to subjects with values that are normal prior to dosing and abnormal after dosing. Potentially clinically significant abnormalities in laboratory analytes are to be reported as TEAEs and summarized as clinical TEAEs.

Subjects with clinical laboratory data meeting the criteria in Section 10 of this SAP for values of potential clinical concern will be flagged and summarized. Proportions of subjects with clinical laboratory values of potential clinical concern will be examined for the treatment groups.

For each post-Baseline assessment, descriptive statistics are provided for the assessment value and the change from Baseline to the assessment with mean, median, standard deviation, minimum, and maximum at each assessment time.

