8.0 ADVERSE EVENT REPORTING

8.1 ADVERSE EVENTS

An adverse event (AE) is any untoward medical occurrence in a clinical study participant administered a pharmaceutical product. Study drug treatment does not necessarily have a causal relationship with the AE. An AE, therefore, can be any unfavorable change in structure, function or chemistry (including abnormal clinical lab results, or ECG findings), symptoms, signs, or diseases temporally associated with the use of a medicinal (investigational) product, whether or not related to the medicinal (investigational) product, as defined by ICH.

The criteria for determining whether an abnormal objective test finding should be reported as an adverse event are as follows:

- Test result is associated with accompanying symptoms, and/or
- Test result requires additional diagnostic testing or medical/surgical intervention, and/or
- Test result leads to a change in study dosing or discontinuation from the study, significant additional concomitant drug treatment, or other therapy, and/or
- Test result is considered to be an adverse event by the investigator or sponsor.

Repeating an abnormal test, in the absence of any of the above conditions, does not constitute an adverse event. Any abnormal test result that is determined to be an error does not require reporting as an adverse event.

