9.3 SAFETY ANALYSIS

A treatment-emergent adverse event (TEAE) is defined as an AE that was not present at baseline, or an exacerbation of a pre-existing AE. For laboratory data, a treatment-emergent abnormal laboratory value (TEAV) represents an abnormal value that was normal at baseline.

Safety variables of analysis include the following:

- Proportions of patients with any TEAEs
- Proportions of patients with serious TEAEs
- Proportions of patients with severe TEAE
- Proportions of patients with TEAEs leading to study drug discontinuation
- Proportions of patients with TEAEs leading to study withdrawal
- Proportions of patients with drug-related TEAEs
- Proportions of patients with TEAVs
- Proportions of patients meeting DILI criteria
- Proportions of patients meeting ICH E14 criteria for threshold values or threshold changes
- Mean changes from baseline in vital signs
- Mean changes from baseline in clinical laboratory measures
- Mean change from baseline in measures from electrocardiography

Continuous data will be summarized by treatment group using descriptive statistics (number, mean, median, standard deviation, first and third quartiles, minimum, and maximum). Categorical data will be summarized by treatment group using frequency tables (frequencies and percentages).

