1.9 Modifications from the Statistical Section of the Protocol

There are no modifications from the Statistical Section of the Protocol.

2 Statistical Hypotheses

There are no formal statistical hypotheses for this open-label study.

3 Populations of Analysis

In accordance with guidance from the International Conference of Harmonization of Technical Requirements for Registration of Pharmaceuticals for Human Use (ICH) guideline ICH E9 Statistical Principles for Clinical Trials (1998), the following population of analysis will be used for all statistical analysis:

- The full analysis set (FAS) includes all randomized subjects who receive any study medication and have at least one post-Baseline assessment.
- The per protocol set (PPS) includes all subjects in the FAS, except for those who are excluded because of major protocol violations, where a major protocol violation is one that may affect the interpretation of study results (e.g., taking less than 50% of prescribed study medication during participation).

Final determinations of the PPS will be made at the final data review meeting (DRM) held in accordance with ICH E9 prior to the lock data.

- The safety set (SAF) includes all patients who received at least one dose of study medication. The SAF is used for all safety analyses.

The FAS is used for efficacy analysis; the SAF will be used for safety analyses.

It is noted that if the FAS and PPS do not differ by more than 15% in numbers of individuals, analysis may be limited to FAS.

4 Variables of Analysis

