4.2.4 Clinical laboratory assessments

Routine clinical laboratory data will be summarized with descriptive statistics on assessment values and change from Baseline. Routine clinical laboratory data will also be evaluated on the basis of laboratory-defined reference ranges and clinically important values or changes, as defined in this document (Section 10). Routinely collected laboratory safety data that are not required by the protocol will be considered source data, and will not be captured for inclusion into the study database. In TTP488-303, the clinical laboratory blood samples will be collected at Months 6, 12, 18 and 24 or in the event of early termination.

Definition:

- A treatment-emergent abnormal value (TEAV) is a laboratory value that is abnormal after administration of study medication that was normal prior to study medication administration.
- A TEAV of potential clinical concern is a value or change that meets criteria specified in this SAP in Section 10.

Laboratory analytes in this study include:

- Hematology
 - Hemoglobin
 - Hematocrit
 - Erythrocyte (RBC) count
 - Platelet count
 - Total leukocyte (WBC) count
 - MCV
 - Leukocyte differential (percent and total)
 - Total neutrophils
 - Eosinophils
 - Monocytes
 - Basophils
 - Lymphocytes
- Clinical chemistry
 - BUN
 - Creatinine
 - Glucose
 - HbA1c
 - Calcium
 - Sodium
 - Potassium
 - Chloride
 - Bicarbonate
 - AST
 - ALT
 - GGT
 - LDH
 - Total bilirubin
 - Alkaline phosphatase
 - Uric acid
 - Albumin
 - Total protein

Safety variables of analysis include:

- Subjects with TEAVs
- Subjects with TEAVs of potential clinical concern (based on criteria in this SAP)
- Subjects with a TEAV in a liver function test (LFT)

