Total bilirubin	>2.5 x ULN (>2.7 mg/dL)
AST	>3 x ULN (>102 U/L)
ALT	>3 x ULN (>123 U/L)
Alk Phosphatase	>3 x ULN (>348 U/L)
Creatinine	>2 mg/dL
BUN	>1.4 x ULN (30.8 mg/dL)
Glucose	≤70 mg/dL or ≥270 mg/dL
Uric acid	>12 mg/dL
Sodium	<125 mmol/L or >155mmol/L
Potassium	<3.0 mmol/L or >6.0 mmol/L
Bicarbonate	<16 mmol/L
Calcium	<6.0 mg/dL and >13.0 mg/dL
Triglycerides	>750 mg/dL
Electrocardiogram	
Heart Rate	<50 bpm and ≥/=25% decrease from baseline >100 bpm and ≥/=25% increase from baseline
PR interval	≥200 msec and ≥25% increase from baseline
QRS interval	≥200 msec and ≥25% increase from baseline
QTc interval	≥500 msec ≥30-60 msec increase >60 msec increase
Vitals (sitting)	
SBP	≥190 mmHg (entry is <180 mmHg) Systolic <80 mm Hg Decrease from baseline ≥30 mmHg
DBP	≥120 mmHg (entry is <105) <50 mm Hg

Parameters not provided with specific thresholds for clinical concern: RBC count, eosinophils, basophils, monocytes, direct or indirect bilirubin (just total as shown above), chloride, albumin, total protein, insulin, total cholesterol, HDL, LDL, urinalysis, pulse rate from VS (rely on ECG heart rate).

11 References

- Berg, L. Clinical Dementia rating (CDR). *Psychopharmacol Bull.* 1988;24:637-9.
- Little, RJA, and Rubin, DB. (1987). *Statistical analysis with missing data.* New York: John Wiley and Sons.
- Rubin, D.B. (1976, December). Inference and Missing data. *Biometrika*, Volume 63, Issue 3 (Dec., 1976), 581-592.
- ICH. (1996, July 30). ICH Harmonized tripartite guideline: Structure and content of clinical study reports (E3). International Conference on Harmonization of Technical Requirements for Registration of Pharmaceuticals for Human Use.
- ICH. (1997, July 17). ICH Harmonized tripartite guideline: General considerations for clinical trials (E8). International Conference on Harmonization of Technical Requirements for Registration of Pharmaceuticals for Human Use.
- ICH. (1998, February 5). ICH Harmonized tripartite guideline: Statistical principles for clinical trials (E9). International Conference on Harmonization of Technical Requirements for Registration of Pharmaceuticals for Human Use.

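### The laboratory TEAV count covers only normal-to-abnormal changes, so moderate worsening from an abnormal baseline need not appear in any subject-level laboratory count

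*SAP*

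**What the plan says.** SAP 4.2.4 defines a TEAV as one that "is a laboratory value that is abnormal after administration of study medication that was normal prior to study medication administration". Protocol 9.3 has the same rule: "a treatment-emergent abnormal laboratory value (TEAV) represents an abnormal value that was normal at baseline". SAP 5.3.3 repeats it, "additional analysis on TEAVs is limited to subjects with values that are normal prior to dosing and abnormal after dosing", and gives the reason: exacerbations "of pre-existing abnormalities in laboratory analytes are examined using clinical judgment and are reported as TEAEs".

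Protocol 8.1 sets out when an abnormal test is an adverse event. It must come with symptoms, lead to further tests or intervention, lead to a change in dosing, participation or therapy, or meet the last condition: "Test result is considered to be an adverse event by the investigator or sponsor".

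The plan has other laboratory analyses, and none of them states a normal-baseline condition:
- flags and proportions for values beyond the Section 10 limits (SAP 5.3.3);
- by-visit descriptive statistics on value and change from baseline (SAP 5.3.3);
- subjects with AST or ALT at least 3 times the upper limit of normal (ULN) and bilirubin at least 2 times ULN (SAP 5.3.4).

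SAP 6.1 takes the safety baseline as the last valid measurement before study drug in TTP488-303. On the analysis set, SAP Section 3 says "The SAF is used for all safety analyses". No denominator is given for TEAV proportions.

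**The concern.** Laboratory tests are part of the primary endpoint (protocol 2.2). The TEAV count can leave out worsening from an abnormal baseline without loss only if adverse event reporting reliably picks that worsening up. The protocol's reporting rule is conditional. A silent rise in an already raised value, with no symptoms and no action taken, need not be reported unless somebody judges it to be an adverse event.

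The choice of baseline adds to this. One of the two displayed groups has had 18 months of azeliragon in TTP488-301 before the TTP488-303 baseline is set. An abnormality that arose on drug during that time becomes an abnormal baseline, and its further worsening is outside the TEAV count. A long-term safety study would want to show such a course subject by subject.

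**Working it through.** The documents give no TEAV rate and no share of subjects abnormal at baseline, so there is no planned figure to reproduce. The check is whether a plausible case can pass through every subject-level laboratory count.

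**Step 1: the range with no flag.** Section 10 gives several limits both as a multiple and as a value, so the implied limit of normal is the value divided by the multiple.

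| Analyte | Section 10 limit | Implied limit of normal | Abnormal but not flagged |
|---|---|---|---|
| ALT | >3 x ULN, >123 U/L | 123/3 = 41 | above 41, up to 123 |
| AST | >3 x ULN, >102 U/L | 102/3 = 34 | above 34, up to 102 |
| Alkaline phosphatase | >3 x ULN, >348 U/L | 348/3 = 116 | above 116, up to 348 |
| Total bilirubin | >2.5 x ULN, >2.7 mg/dL | 2.7/2.5 = 1.08 | above 1.08, up to 2.7 |
| Platelets | <0.5 x LLN (lower limit), <70 | 70/0.5 = 140 | below 140, down to 70 |

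SAP 4.2.4 says that Section 10 covers values or changes, but every laboratory row is an absolute limit. Change from baseline is used only for ECG measures and systolic pressure.

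**Step 2: one subject traced through.** ALT goes from 50 U/L (50/41 = 1.22 x ULN) to 120 U/L (120/41 = 2.93 x ULN).
- TEAV: no, because the baseline was abnormal.
- Section 10 flag: no, because 120 does not exceed 123.
- Liver criterion: no, because 120 is below 3 x 41 = 123.
- By-visit summaries: yes, but these show means and extremes for the group. They do not count subjects or show baseline status.
- Adverse event: only if a protocol 8.1 condition is met.

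At 130 U/L the same subject would be flagged by Section 10 despite the abnormal baseline.

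**Step 3: analytes with no limit.** HbA1c, GGT and LDH are measured (protocol 7.1.5.1, SAP 4.2.4) but have no row in Section 10. They are also missing from its closing note of exempt parameters, which begins "Parameters not provided with specific thresholds for clinical concern: RBC count, eosinophils, basophils, monocytes". For these three, and for the measured analytes that the note does exempt, no worsening from an abnormal baseline can be flagged, however large.

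**Step 4: how much a TEAV count alone could miss.** For one analyte, let q be the share abnormal at baseline, p the normal-to-abnormal rate among the rest, and w the worsening rate among those abnormal at baseline. The share of all such events outside the TEAV count is wq / [p(1 - q) + wq]. With assumed p = 10% and w from 5% to 20%:
- q = 5%: 2.6% to 9.5%
- q = 15%: 8.1% to 26.1%
- q = 30%: 17.6% to 46.2%

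All three inputs are assumptions. Section 10 flags and adverse event reports would recover some of these events, so the figures are upper bounds on what is missed altogether.

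**Step 5: the denominator.** If TEAV proportions use only subjects normal at baseline, the reported rate is p. If they use the whole safety set (SAF), it is p(1 - q). The documents do not say which applies.

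**The case against.** The best defence is that the plan relies on judgment and allows for it. Protocol 8.1 includes investigator or sponsor judgment, and its definition of an adverse event reaches abnormal laboratory results. Protocol 8.2 treats worsening of pre-existing conditions after the first dose as an adverse event. SAP 4.2 has medically qualified staff review the listings, and SAP 5.3.3 expects potentially significant abnormalities to be reported as adverse events. Protocol 7.1.5.2 deals separately with raised baseline AST or ALT. This stands for marked or clinically active worsening. It does not give a rule by analyte for moderate, silent worsening. Nor can SAP text change what sites were told to report: SAP 1.5 records that the study had already been terminated. The protocol 8.1 sentence "Repeating an abnormal test, in the absence of any of the above conditions, does not constitute an adverse event" concerns repeat testing, so the point does not rest on it.

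A reader might infer more than the documents support:
- **That TEAV rates are diluted.** This would follow only if all safety-set subjects form the denominator. Section 3 names the analysis set, and the wording of 5.3.3 can equally be read as an at-risk group, with no dilution.
- **That laboratory worsening in general is under-counted.** Section 10 flags, by-visit changes and the liver criterion apply whatever the baseline.
- **That a subject with one abnormal baseline value is lost from the whole analysis.** The definition concerns a value, so it works analyte by analyte.
- **That the SAP departs from the protocol.** Protocol 9.3 has the same definition.
- **That one group is favoured.** No TTP488-301 laboratory data are given, so neither direction nor size can be stated.

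**Conclusion.** The point holds in a limited form. Worsening from an abnormal baseline that stays inside the Section 10 limits, or that occurs in HbA1c, GGT or LDH, can be absent from every subject-level laboratory count. It then shows only in by-visit summaries. The reason given in SAP 5.3.3 for accepting this is stronger than protocol 8.1 allows.

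The gap is certain as a matter of definition; how many subjects fall into it is unknown. It depends on how many values are abnormal at baseline, how often they worsen, and how much of that worsening sites reported as adverse events. Any imbalance between the two displayed groups is a possibility created by the choice of baseline and has not been shown. The unstated denominator is a separate omission that needs one sentence. This is a cheap improvement to a descriptive analysis of a primary safety endpoint.

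**What to change.** In the SAP:
- **5.3.3:** add, for every analyte including HbA1c, GGT and LDH, a table of baseline category against worst on-treatment category. Use bands in multiples of the limit of normal (for example up to 1, 1 to 1.5, 1.5 to 2, 2 to 3 and above 3 x ULN, with matching bands below the lower limit). Include all safety-set subjects with a baseline and a post-baseline value, by former randomised group and overall.
- **4.2.4 and 5.3.3:** state that each TEAV proportion is computed per analyte among subjects normal at baseline with at least one post-baseline value.
- **5.3.3:** reword the premise so that worsening of a pre-existing abnormality is described as reported when it meets protocol 8.1.
- **Section 9:** add the new tables to the planned laboratory displays.

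The cost is some SAP wording and a few standard tables. The data are already collected, and protocol 9.0 lets the SAP supersede its statistical section, so no protocol change is needed.
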